8.1.9.3. Concomitant Medications

Concomitant medication verbatim terms in the eCRFs will be mapped to Anatomical/Therapeutic/Chemical (ATC) class and Preferred Names using WHODrug Global.

Concomitant medications will be summarized by ATC class and preferred name. These summaries will present the number and percentage of patients using each medication. Patients may have more than 1 medication per ATC class and preferred name. At each level of summarization, a patient will be counted only once if he/she reported 1 or more medications at that level.

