Statistical Methods:	
Presentation of PK and safety data will be produced for the PK Population and Safety Population, respectively.
 
A PK Population model will be developed using data from the completed Phase 1 study of single-ascending/multiple-ascending doses in normal healthy volunteers (Study SPR720-101). This population model will be used to estimate PK parameters for patients in the SPR720-201 study.
 
Dates and times of blood samples as well as dates and times of study drug administration will be recorded. Plasma concentration-time data from intensive PK sampling patients will be subjected to noncompartmental PK analysis. Day 1 and Day 28 PK parameters including, but not limited to, C_{max}, T_{max}, area under the concentration-time curve from zero to last concentration (AUC_{last}), AUC_{0-t}, accumulation ratio, and plasma concentration at the end of a dosing interval at steady state (taken directly before next administration) (C_{trough}) will be determined for SPR719. Concentration data from sparse sampling will be compiled for summary statistics of C_{trough} across various days. Concentration data from SPR720 recipients will be used for the development of a PK Population model, for PK analysis, and for estimation of individual PK profiles in patients with sparse sampling, which will be reported in a separate report.
 
Patient disposition, demographics and baseline characteristics, IP exposure, and prior and concomitant medications will be summarized.
 
All safety presentations will be descriptive, and all summaries will be displayed by treatment arm. Summary statistics for continuous variables will include the sample size, mean, standard deviation, minimum, median, and maximum. For categorical data, summaries will include the frequency and percentage. The incidence and frequency of AEs and serious AEs will be summarized by treatment arm by severity and relationship. Laboratory results will be summarized by treatment arm for each time point and change from baseline at each postbaseline time point. Frequency and percentage for laboratory tests that are considered CS and out of range will be presented. In addition, shifts from baseline using CTCAE v5.0 by treatment arm for selected laboratory tests (aspartate aminotransferase, alanine aminotransferase, gamma-glutamyltransferase, alkaline phosphatase, total bilirubin, amylase, lipase, blood urea nitrogen, serum creatinine, creatinine clearance, hemoglobin, hematocrit, neutrophils, lymphocytes, and erythrocytes) will be presented. Vital signs and 12-lead ECG parameters will be summarized and will include change from baseline. Twelve-lead ECGs including QTc intervals will also be summarized as clinically meaningful changes in physical examination findings.
  

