4.2. Dosage Schedule

Dosing for each treatment arm is displayed in [Table 1](#). Study drug will be taken po once daily for 28 days (Days 1 through 28). Dosing for Treatment Arms 1, 2, and 3 will take place at the clinic on study visit days. The clinic and patient should try to schedule clinic visits as early as possible in the morning to accommodate pre-dose study activities and dosing, preferably before a meal. Patients in Treatment Arms 1, 2, and 3 should make every effort to take the IP at the same time in the morning approximately an hour before a morning meal on an empty stomach. There are no liquid restrictions. Patients will receive a supply of IP and instructions for documenting at-home dosing. If a patient experiences IP tolerability issues while at home, the site should instruct the patient to call the Investigator. The Investigator may instruct the patient to take their dose with a snack or meal, if clinically indicated, to alleviate tolerability concerns. Dosing for Treatment Arm 4 (SOC) should occur per specific prescribing information instructions.

Table 1: Study Treatments

Treatment Arm 1	Double-blinded SPR720 IP 500 mg (2 capsules of 250 mg SPR720 and 2 capsules of placebo) po once daily
Treatment Arm 2	Double-blinded SPR720 IP 1000 mg (4 capsules of 250 mg SPR720) po once daily
Treatment Arm 3	Double-blinded placebo (4 capsules of placebo) po once daily
Treatment Arm 4	
Standard of Care regimen is at the Investigator's discretion; recommended 2-drug or 3-drug SOC, consisting of either:
 
 • Clarithromycin 500-1000 mg, plus ethambutol HCl 15 mg/kg po once daily or • Azithromycin 250-500 mg, plus ethambutol HCl 15 mg/kg po once daily 
Optional rifampin 600 mg or rifabutin 300 mg po once daily may be added to the SOC regimen for up to 28 days.
 
Inform the medical monitor of alternative SOC regimens and discuss concerns or questions.

Abbreviations: HCl=hydrochloride; IP=investigational product; po=orally; SOC=standard of care.

Note: Patients will be treated for 28 days.

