4.7.2. Concomitant Treatments

Concomitant medications and treatments, defined as treatments taken after the first dose of IP and SOC, should be recorded in the eCRF according to completion guidelines. Medications and treatments taken before the first dose of IP or SOC will not be recorded in the eCRF.

Patients should not have used any systemic (po or IV) or inhaled antibiotic with activity versus MAC between screening and randomization. Drugs or supplements that are strong CYP3A4 enzyme inducers or inhibitors (see [Appendix 1](#)) within 4 weeks of randomization and during the study are prohibited. Hepatic transporters, OATP1B1 or OATP1B3, (see [Appendix 2](#)) within 1 week of randomization and during the study are prohibited.

Any medication or therapy that is taken by or administered to the patient during the study will be recorded (see completion guidelines for eCRF).

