8.1.2. Secondary

- Reported AEs
- Clinically meaningful change in physical examination findings
- Concomitant medication usage
- Changes from baseline in laboratory tests
- Clinically significant out-of-normal range laboratory tests
- Shifts from baseline for selected laboratory tests using National Cancer Institute CTCAE v5.0 shift categories
- Changes from baseline in vital sign measurements (body temperature, heart rate, respiratory rate, blood pressure)
- 12-lead ECGs

[REDACTED]

- | [REDACTED]
- | [REDACTED]
- | [REDACTED]
- | [REDACTED]
- | [REDACTED]
- | [REDACTED]
- | [REDACTED]
- | [REDACTED]
- | [REDACTED]

[REDACTED]

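### The concomitant-medication safety summary counts continued long-term treatment the same as a new start, which dilutes any SPR720 versus placebo difference in newly started medication

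*Combined protocol and SAP*

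**What the plan says.** - **Endpoint.** Section 8.1.2 and the Synopsis list "Concomitant medication usage" among the secondary safety endpoints.
- **Definition.** In Section 4.7.2, concomitant medications and treatments are "defined as treatments taken after the first dose of IP and SOC". There is no condition on when the treatment began. The same section adds: "Any medication or therapy that is taken by or administered to the patient during the study will be recorded".
- **Analysis.** Section 8.1.9.3 summarizes by ATC class and preferred name: "These summaries will present the number and percentage of patients using each medication". On counting it says: "At each level of summarization, a patient will be counted only once if he/she reported 1 or more medications at that level". Nothing separates treatment carried over from before Day 1 from treatment started or increased afterwards, and the reason for use plays no part.
- **Prior medication.** Section 4.7.2 states: "Medications and treatments taken before the first dose of IP or SOC will not be recorded in the eCRF". The Synopsis (Statistical Methods) states that "prior and concomitant medications will be summarized". The two do not agree.
- **SOC drugs.** The Arm 4 regimen appears in Section 4.2 under "Table 1: Study Treatments". Section 4.6 has SOC doses taken at home logged in the same diary as investigational product (IP) doses.

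**The concern.** As a safety measure, medication use is informative mainly through what is newly started or increased on study, because that may reflect a symptom prompted by study drug. A count of any use mixes this with background treatment. Background use is plausibly high here: Section 1.1.1 describes underlying COPD and bronchiectasis, Section 1.1.2 describes daily nebulizer treatment, and eligibility requires at least two symptoms.

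The rest of the safety plan is tied to baseline. A treatment-emergent adverse event needs onset or worsening on or after the first dose (Section 8.1.9.2), and laboratory, ECG and vital-sign data are analysed as change from baseline (Sections 8.1.9.4 to 8.1.9.6). Concomitant medication has no such reference. If Section 4.7.2 governs, there is also no record of medication used only before dosing against which to read the percentages. At stake is the legibility of one descriptive safety table, not a formal conclusion.

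**Working it through.** The plan gives no rate, test or sample-size calculation for this endpoint, so there is no planned figure to reproduce. The check below is an illustration.

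**Inputs from the documents.** Section 3.1 gives 19 to 20 patients per arm at sparse PK sites plus 6 at intense PK sites, so 25 to 26 in each of Arms 1, 2 and 3. I use n = 25.

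**Assumed inputs.** b is the share already using a drug in a given row (ATC class or preferred name), equal in both arms on average. s0 and s1 are the new-start rates among the rest on placebo and SPR720. None of these is in the documents.

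**Formula.** Under the counting rule, P(any use) = b + (1-b)s. The between-arm difference is (1-b)(s1-s0). A patient already in the row adds nothing by starting a second drug in it.

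**Any-use table, s0 = 5%, s1 = 25% (20 points among non-users):**

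| b | Placebo | SPR720 | Difference (points) | Ratio |
|---|---|---|---|---|
| 0% | 5.0% | 25.0% | 20 | 5.0 |
| 10% | 14.5% | 32.5% | 18 | 2.24 |
| 30% | 33.5% | 47.5% | 14 | 1.42 |
| 50% | 52.5% | 62.5% | 10 | 1.19 |
| 70% | 71.5% | 77.5% | 6 | 1.08 |
| 90% | 90.5% | 92.5% | 2 | 1.02 |

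**Noise at b = 60%, s0 = 0, s1 = 20%.**
- Any use: 0.60 + 0.40 × 0.20 = 0.68 against 0.60. SE = √(0.68×0.32/25 + 0.60×0.40/25) = 0.135. Difference/SE = 0.08/0.135 = 0.59.
- New starts over all patients in the arm: 0.40 × 0.20 = 0.08 against 0. SE = √(0.08×0.92/25) = 0.054. Difference/SE = 1.47, about 2.5 times as large.

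The zero placebo rate flatters the second figure, because that arm then contributes no variance.

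**Noise at b = 60%, s0 = 5%, s1 = 25%.**
- Any use: 0.70 against 0.62. SE = √(0.70×0.30/25 + 0.62×0.38/25) = 0.134. Difference/SE = 0.60.
- New starts over all patients: 0.40 × 0.25 = 0.10 against 0.40 × 0.05 = 0.02. SE = √(0.10×0.90/25 + 0.02×0.98/25) = 0.066. Difference/SE = 1.21, about twice as large.

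With whole-arm denominators, both tables show the same 8 points. The gain from the split is the smaller SE and the clearer contrast: 10% against 2%, rather than 70% against 62%.

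**The case against.** **Randomization and blinding.** Continued use should balance on average between SPR720 and placebo, so the comparison is not biased. This stands. Balance on average does not remove the dilution or the chance variation with about 25 patients per arm.

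**Other views exist.** New or worsening illness after first dose is an adverse event (Section 4.7.1), measures applied for adverse events go into the eCRF as applicable (Section 6.4), all data are listed by patient (Section 8), and a preferred-name row can show a new drug even when its class was already in use. This stands. A reader might infer that the table hides treatment prompted by study drug, or that background use swamps any effect; the documents do not support either. But listings are not a by-arm summary of this endpoint.

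**No inference depends on it.** No formal hypothesis is planned (Section 8.1.4), safety is descriptive (Section 8.1.9), and even after the split the illustrative ratios stay below 2. This limits the importance of the point and does not refute it.

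**Unseen material may cover it.** The eCRF completion guidelines may collect start dates, and Section 8 promises a detailed SAP before database lock. That is possible, but the analysis in the documents is Section 8.1.9.3, and a data field has to be in place before data entry.

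**Arm 4.** A reader might also infer that assigned SOC drugs enter this table and fill its rows to near 100%. The documents do not say so. SOC is listed as study treatment, logged with IP, and used as a reference dose in the definition of concomitant treatment. Rifampin or rifabutin is optional, and the macrolide may be either of two. The Safety Population requires receipt of IP (Section 8.1.5), which Section 4.1 defines, for that section, as SPR720 and placebo; read literally, Arm 4 may not be in the table. Its rows could not in any case mask a difference between SPR720 and placebo. What remains is that the plan does not state how SOC drugs are handled here.

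**Conclusion.** The point holds as a low-severity improvement. As written, the endpoint counts any use after first dose, so continued long-term treatment and new starts are indistinguishable. A difference in new starts among non-users is scaled by (1-b): a 20-point difference becomes 18 points at b = 10%, 8 at b = 60% and 2 at b = 90%. Separating new starts would raise the difference-to-SE ratio about 2 to 2.5 times at b = 60% and 25 patients per arm. These sizes rest on assumed rates, on equal prior use in both arms, and on existing users adding nothing further in the row. Where prior use is rare, as it may be for many preferred names, the loss is small. The conflict between the Synopsis and Section 4.7.2 on prior medication is a matter of text and rests on no assumption.

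**What to change.** 1. In Section 8.1.9.3, use the eCRF start date, or a flag for ongoing at first dose, to present by arm (a) medications ongoing at first dose and (b) medications started on or after first dose. Name (b) as the safety summary and state its denominator.
2. If dose increases of existing drugs are to count, add a separate flag; a start-date split alone will miss them.
3. Reconcile the Synopsis, which summarizes prior medications, with Section 4.7.2, which does not record medication taken before the first dose. Make clear that a drug begun earlier and continued is recorded with its start date or flag.
4. State that assigned SOC drugs are reported as study treatment and left out of this table, and clarify whether Arm 4 belongs to the Safety Population.

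The cost is one extra table, one eCRF field if it is not already collected (a second if dose increases are flagged), and a few sentences of text. No patient procedure is added.

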8.1.9.4. Laboratory Data

Laboratory results (hematology, serum chemistry, and urinalysis) will be summarized by treatment arm for each time point, change from baseline at each postbaseline time point, shifts from baseline for selected laboratory tests (aspartate aminotransferase, alanine aminotransferase, gamma-glutamyltransferase, alkaline phosphatase, total bilirubin, amylase, lipase, blood urea nitrogen, serum creatinine, creatinine clearance, hemoglobin, hematocrit, neutrophils, lymphocytes, and erythrocytes) using CTCAE v5.0, and CS out-of-normal range laboratory. In addition, scatterplots of key laboratory values over time will also be produced.

8.1.9.5. Electrocardiographic Data

Baseline and change from baseline in ECG parameters (heart rate, cardiac rhythm, PR interval, RR interval, QRS interval, QT interval, and QTc interval) will be summarized at each postbaseline time point. At each time point, the number of patients with QTc according to Fridericia's formula (QTcF) values of >450 ms, >480 ms, and >500 ms will be presented. At each postbaseline time point, the number of patients with change from baseline values in QTcF of >30 ms and >60 ms will be presented.

8.1.9.6. Vital Signs

Summary statistics for the absolute vital sign value and the changes from baseline will be presented by treatment arm for each visit.

8.1.9.7. Physical Examinations

Clinically meaningful changes in physical examination findings will be identified and summarized by treatment arm.

[REDACTED]

[REDACTED]

[REDACTED]

[REDACTED]

[REDACTED]

9. STUDY MANAGEMENT

9.1. Regulations and Guidelines

The study will be performed in accordance with this protocol, US investigational new drug regulations (US Title 21 Code of Federal Regulations [CFR] Part 312), International Council for Harmonisation of Technical Requirements for Pharmaceuticals for Human Use (ICH) guidelines for Good Clinical Practice (GCP), and the regulations on electronic records and electronic signature (Title 21 CFR Part 11).

9.2. Sponsor's Responsibilities

9.2.1. Good Clinical Practice

The Sponsor and any third party to whom aspects of the study management or monitoring have been delegated will undertake their assigned roles for this study in compliance with all applicable industry regulations and ICH GCP Guideline E6(R2).

Representatives of the Sponsor and/or the company organizing/managing the research on behalf of the Sponsor to inspect study data, patients' medical records, and eCRFs in accordance with current GCP and the respective government regulations and guidelines conduct visits to sites. Records and data may additionally be reviewed by auditors or by regulatory authorities.

The Sponsor ensures that local regulatory authority requirements are met before the start of the study. The Sponsor (or designee) is responsible for the preparation, submission, and confirmation of receipt of any regulatory authority approvals required prior to release of IP for shipment to the site.

9.2.2. Indemnity/Liability and Insurance

The Sponsor ensures that suitable clinical study insurance coverage is in place prior to the start of the study. An insurance certificate is supplied to the CRO/Investigator as necessary.

9.2.3. Public Posting of Study Information

The Sponsor is responsible for posting appropriate study information on applicable websites. Information included in clinical study registries may include participating Investigators' names and contact information.

9.2.4. Suspension, Discontinuation, and Completion of the Study

The Sponsor reserves the right to suspend or discontinue the study or part of the study at any time for any reason. If the study is suspended or terminated, the Sponsor will ensure that applicable regulatory agencies and IRBs are notified as appropriate. Additionally, the discontinuation of a registered clinical study, which has been posted to a designated public website, will be updated accordingly. Should the study be terminated and/or a site closed, all IP pertaining to the study must be returned to the Sponsor or its representative.

9.3. Investigator Responsibilities

9.3.1. Good Clinical Practice Compliance

The Investigator must undertake to perform the study in accordance with ICH GCP Guideline E6(R2) and applicable regulatory requirements and guidelines.

It is the Investigator's responsibility to ensure that adequate time and appropriately trained resources are available at the site prior to commitment to participate in this study. The Investigator should also be able to estimate or demonstrate a potential for recruiting the required number of suitable patients within the agreed recruitment period.

The Investigator will maintain a list of appropriately qualified persons to whom the Investigator has delegated significant study-related tasks. *Curricula vitae* for Investigators and Subinvestigators will be provided to the Sponsor (or designee) before starting the study.

If a potential research patient has a primary care physician, the Investigator should, with the patient's consent, inform them of the patient's participation in the study.

9.3.2. Protocol Adherence and Investigator Agreement

The Investigator and any Subinvestigators must adhere to the protocol as detailed in this document. The Investigator is responsible for enrolling only those patients who have met protocol eligibility criteria. Investigators are required to sign an Investigator Agreement to confirm acceptance and willingness to comply with the study protocol.

If the Investigator suspends or terminates the study at their site, the Investigator will promptly inform the Sponsor and the IRB and provide them with a detailed written explanation. The Investigator will also return all IP, containers, and other study materials to the Sponsor. Upon study completion, the Investigator will provide the Sponsor, IRB, and regulatory agency with final reports and summaries as required by national regulations.

Communication with local IRBs, to ensure accurate and timely information is provided at all phases during the study, may be done by the Sponsor, CRO, or Investigator.

9.3.3. Institutional Review Board

Conduct of the study must be approved by an appropriately constituted IRB, which operates in accordance with the principles and requirements described in the US Title 21 CFR Part 56, and the ICH guidelines. Approval is required for the study protocol, protocol amendments, ICFs, patient information sheets, and advertising materials.

9.3.4. Informed Consent

For each trial patient, a written ICF will be obtained before any protocol-specific activities are performed. As part of this procedure, the Investigator or a designated representative must explain orally and in writing the nature, duration, and purpose of the study, and the action of the IP in such a manner that the patient and (if applicable) appointed guardian are aware of the potential risks, inconveniences, or adverse effects that may occur. Patients should be informed that they may withdraw from the study at any time. They will receive all information that is required by federal regulations and ICH guidelines. The Principal Investigator or a designated representative

will provide the Sponsor or its representative with a copy of the approved ICF before the start of the study.

The Sponsor's indemnification of the Investigator and institution during the conduct of this study will be discussed in a separate document.

9.4. Study Documentation

By signing a copy of Form FDA 1572, the Principal Investigator acknowledges that he/she has received a copy of the IB on SPR720 and assures the Sponsor that he/she will comply with the protocol and the provisions stated in Form FDA 1572. No changes in this protocol can be made without the Sponsor's written approval.

9.5. Data Management and Quality Control

9.5.1. Electronic Case Report Forms

Electronic case report forms will be used to collect all patient data during the study. The Investigator is responsible for the accuracy and completeness of all data in the eCRFs.

The Investigator is responsible for maintaining adequate and accurate medical records from which accurate information is recorded into the eCRFs, which have been designed to record all observations and other data pertinent to the clinical investigation. The Investigator or designee as stated in the site delegation log must complete eCRFs.

9.5.2. Recording, Access, and Retention of Source Data and Study Documents

Original source data to be reviewed during this study will include, but is not limited to the patient's medical file, patient diaries, original clinical laboratory reports, and histology and pathology reports. All key data must be recorded in the patient's medical records.

The Investigator must permit authorized representatives of the Sponsor, the respective national, local, or foreign regulatory authorities, the IRB, and auditors to inspect facilities and to have direct access to original source records relevant to this study, regardless of media.

The Study Monitor (and auditors, IRB or regulatory inspectors) may check the eCRF entries against the source documents. The consent form includes a statement by which the patient agrees to the monitor/auditor from the Sponsor or its representatives, national or local regulatory authorities, or the IRB having access to source data (e.g., patient's medical file, appointment books, original laboratory reports, X-rays).

These records must be made available within reasonable times for inspection and duplication, if required, by a properly authorized representative of any regulatory agency (e.g., the FDA or an auditor).

Essential documents must be maintained according to ICH GCP requirements and may not be destroyed without written permission from the Sponsor.

